Humalog U-200 KwikPen is a prefilled and multi-dose pen-injector device (pen) that delivers insulin lispro by subcutaneous injection to improve glycemic control in adults and children with diabetes mellitus. Compared to Humalog U-100 KwikPen, it contains the same number of units of insulin lispro in half the volume. Despite warning messages on the pen and in the instructions for use, results from Human Factors studies performed in the United States (US) showed that a small percentage of patients may choose to withdraw insulin from the pen cartridge with a syringe if faced with device malfunction. Anecdotal information also indicates that patients may transfer insulin lispro from the pen cartridge into an insulin pump. Because of these data and to further optimize the benefit-risk balance of the presentation, additional Risk Minimization Measures beyond routine risk minimization measures (are being implemented, including communications to Healthcare Professionals (HCPs) and patients to minimize the risk of hyperglycemia and/or potentially hypoglycemia associated with insulin transfer from the pen cartridge to an alternative administration device without concentration adjustment and dose adjustment when transferring from Humalog U-100 KwikPen to Humalog U-200 KwikPen.

The additional Risk Minimization Measures will include a Direct Healthcare Professional Communication (DHPC) that will be distributed to pharmacists and prescribers (endocrinologists and mealtime insulin prescribing primary care physicians, nurse practitioners, and physician's

assistants). A patient communication document will be distributed in the single pen product sample packages that are routinely provided by HCPs to patients who have been newly prescribed Humalog U-200 KwikPen.

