5.3. Study Endpoints

The additional Risk Minimization Measures will be considered effective if the majority of respondents demonstrate they are aware of the key safety messages communicated.

HCPs:

- Demonstrating that they understand the key safety messages communicated in the DHPC.
- Reporting they discuss the safe use of the product as defined in the product label and DHPC to their patients who are receiving their first prescription of Humalog U-200 KwikPen.

Patients:

- Demonstrating that they understand the key safety messages communicated about Humalog U-200 KwikPen.
- Reporting that they follow the key safety messages during administration of Humalog U-200 KwikPen.

All statistical analyses will be descriptive, i.e., no formal hypothesis will be tested.

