[DROP DOWN LIST INPUT WITH STATES TABLE, EXCLUDE PREFER NOT TO ANSWER]

[IF RESPONDENT ANSWERS MASSACHUSETTS, MINNESOTA, VERMONT, OR DISTRICT OF COLUMBIA, DISPLAY REMINDER MESSAGE 1 ON SAME PAGE AND GO TO Q4.]

[REMINDER MESSAGE 1]: If you practice and you are licensed in the District of Columbia, Massachusetts, Minnesota, or Vermont just a reminder that we appreciate your participation; however, no compensation for your services will be provided in accordance with local laws.

4. Please choose an option about your participation in this survey.
 - i. ○ I will participate in the survey and provide my contact information.
 - ii. ○ I will participate in the survey but choose not to be paid.

5. Are you involved in the management of patients with diabetes? This includes prescribing medications to treat diabetes or providing education to help manage diabetes.
- Yes
 - No **[GO TO Q7, TERMINATE AFTER Q14]**
6. What is your role in the management of patients with diabetes?
- Physician
 - Nurse Practitioner
 - Physician Assistant
 - Registered Nurse **[GO TO Q8]**
 - Other **[GO TO Q8]**
7. What is your primary medical specialty?
- General Internal Medicine
 - Endocrinology/Diabetology
 - Family Medicine
 - Other
8. How many years have you been in practice as a physician, physician assistant, or nurse since completing your medical/nursing education?
- Less than 5 years
 - 5 – 10 years
 - 11 – 15 years
 - More than 15 years

9. In what type of facility do you work?
- General Practice
 - Hospital
 - Other
10. Are you aware of the insulin product Humalog® U-200 KwikPen®?
- Yes
 - No **[GO TO Q12, TERMINATE AFTER Q14]**
 - I don't know **[GO TO Q12, TERMINATE AFTER Q14]**
11. For how many patients have you prescribed, or managed their treatment with, Humalog® U-200 KwikPen®?
- 0 **[TERMINATE AFTER QUESTION 14 IF 140 OR MORE COMPLETE RESPONDENTS HAVE ANSWERED 0, WHERE 140 IS A CONFIGURABLE NUMBER]**
 - 1 – 5
 - 6 – 10
 - 11 – 20
 - More than 20

12. Have you or any of your immediate family members ever worked for Eli Lilly and Company (Lilly), United BioSource Corporation (UBC), or the Food and Drug Administration (FDA)?

- Yes **[TERMINATE AFTER QUESTION 14]**
- No
- I don't know **[TERMINATE AFTER QUESTION 14]**

13. Which of the following groups best describes your age?

- Less than 30
- 30 – 39
- 40 – 49
- 50 – 59
- 60 – 69
- 70 or older

14. What is your gender?

- Male
- Female

[END SCREENING QUESTIONS]

[BEGIN SURVEY CONTENT]

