[BEGIN PREAMBLE 2 – DISPLAY ON SAME PAGE AS NEXT QUESTION]

The following questions are about Humalog® U-200 KwikPen®.

[END PREAMBLE 2]

15. Please answer True, False, or I don't know for each of the following statements regarding Humalog® U-200 KwikPen®.

	[RANDOMIZE LIST]	True	False	I don't know
A	Humalog® U-200 KwikPen® is approved for transfer to syringe or pump.			
B	The dose of insulin does not need to be converted when changing patients from one Humalog strength to the other (for example, changing a patient from Humalog U-100 units/mL to Humalog® U-200 KwikPen®).			
C	When prescribing Humalog® U-200 KwikPen®, it is important to clearly indicate the correct strength on the prescription.			
D	It is important to instruct your patients that they should always have a backup pen available.			

16. Are you aware of the Direct Healthcare Professional Communication provided to you by Eli Lilly and Company on the correct use of Humalog® U-200 KwikPen® (*insulin lispro*) to minimize medication errors?

- Yes
- No **[GO TO Q18]**
- I don't know **[GO TO Q18]**

17. Did you read the Direct Healthcare Professional Communication provided to you by Eli Lilly and Company on the correct use of Humalog® U-200 KwikPen® (*insulin lispro*) to minimize medication errors?
- Yes
 - No
 - I don't know
18. Are you aware of the patient communication Patient Information Letter/*IMPORTANT SAFETY INFORMATION FOR* Humalog® U-200 KwikPen® (*insulin lispro*) that is included in patient sample packs of Humalog® KwikPen® provided by Eli Lilly and Company?
- Yes
 - No **[GO TO Q20]**
 - I don't know **[GO TO Q20]**
19. Have you read the patient communication: Patient Information Letter/*IMPORTANT SAFETY INFORMATION FOR* Humalog® U-200 KwikPen® (*insulin lispro*) provided by Eli Lilly and Company?
- Yes
 - No
 - I don't know

[DO NOT DISPLAY QUESTION 20 IF 0 IS SELECTED IN QUESTION 11]

20. Do you or another healthcare professional at your practice discuss the safe use of the Humalog® U-200 KwikPen® to patients receiving their initial prescription?
- Yes
 - No
 - I don't know

[DO NOT DISPLAY QUESTION 21 IF 0 IS SELECTED IN QUESTION 11]

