21. Do you or another healthcare professional at your practice discuss the Patient Information Letter/*IMPORTANT SAFETY INFORMATION FOR* Humalog® U-200 KwikPen® (*insulin lispro*) with patients at the time of initial prescription of Humalog® U-200 KwikPen®?
- Yes
 - No
 - I don't know

[TELEPHONE: BEGIN SAFETY EVENT – KEEP ON ONE PAGE]

(INTERVIEWER: Please record if respondent spontaneously reported a safety event or product complaint during the course of this interview.)

- Yes
- No

Enter Safety Event or Product Complaint Verbatim

[MULTILINE INPUT]

(INTERVIEWER: Indicate to the respondent that someone may call back to ask more questions about the adverse event or product complaint that was reported.)

[TELEPHONE: END SAFETY EVENT]

[BEGIN CLOSING 1]

[DISPLAY CLOSING 1 IF QUESTION 4= i.]

We would like to send you \$100 as compensation for your time and effort as well as a copy of the Dear Healthcare Professional Communication (DHPC) for Humalog® U-200 KwikPen®, and the correct answers to key safety message questions, but need your name and address to do so. Do you agree to provide your contact information for this purpose?

- Yes **[IF SELECTED, DISPLAY CONTACT INFORMATION ON SAME PAGE]**
- No **[GO TO CLOSING 3]**

[END CLOSING 1]

[BEGIN CLOSING 2]

[DISPLAY CLOSING 2 IF QUESTION 3= MASSACHUSETTS, MINNESOTA, DISTRICT OF COLUMBIA OR VERMONT OR QUESTION 4 = ii OR IF NO TO CLOSING 1.]

Do you agree to give us your name and mailing address so we can send you a copy of the Dear Healthcare Professional Communication (DHPC) for Humalog® U-200 KwikPen®, as well as the correct answers to key safety message questions?

- Yes **[IF SELECTED, DISPLAY CONTACT INFORMATION ON SAME PAGE]**
- No **[GO TO CLOSING 3]**

[END CLOSING 2]

[BEGIN CONTACT INFORMATION]

FIRST NAME: **[FREE TEXT]**

LAST NAME: **[FREE TEXT]**

MIDDLE INITIAL: **[OPTIONAL; MUST BE 1 ALPHA CHARACTER]**

ADDRESS: **[MULTILINE INPUT]**

CITY: **[FREE TEXT]**

STATE: **[DROP-DOWN LIST INPUT WITH STATES TABLE]**

ZIP CODE: **[MUST BE 5-DIGIT NUMERIC ONLY]**

[END CONTACT INFORMATION]

[BEGIN CLOSING 3]

This completes the survey. Thank you again for your participation.

[END CLOSING 3]

[END SURVEY CONTENT]

HEALTHCARE PROFESSIONAL CORRECT ANSWER DOCUMENT

**Correct Responses to PRESCRIBER Survey Questions about
Key Safety Messages for Humalog® U-200 KwikPen®**

Q: Please answer True, False, or I don't know for each of the following statements regarding Humalog® U-200 KwikPen®.

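### HCP survey Q20 and Q21 cannot separate practices that do not counsel from practices with no first U-200 prescriptions, so the behaviour rates can be understated by an unknown amount

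*Protocol*

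**What the plan says.** Protocol section 5.3 sets the HCP behaviour endpoint as HCPs reporting that they discuss safe use "to their patients who are receiving their first prescription of Humalog U-200 KwikPen". Two items in Appendix I.1 measure it.

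- Q20 asks: "Do you or another healthcare professional at your practice discuss the safe use of the Humalog® U-200 KwikPen® to patients receiving their initial prescription".
- Q21 asks whether the patient letter is discussed "with patients at the time of initial prescription of Humalog® U-200 KwikPen".

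Both items offer only Yes, No and I don't know. The routing rules are "DO NOT DISPLAY QUESTION 20 IF 0 IS SELECTED IN QUESTION 11" and "DO NOT DISPLAY QUESTION 21 IF 0 IS SELECTED IN QUESTION 11". The gate, Q11, reads: "For how many patients have you prescribed, or managed their treatment with, Humalog® U-200 KwikPen". One managed patient is enough to be asked both items.

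Section 5.11.1 requires every presented question to be answered, and section 5.8 allows missing data only through skip patterns. On the letter, section 3.1 says: "A patient communication document will be distributed in the single pen product sample packages that are routinely provided by HCPs to patients".

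**The concern.** The endpoint refers to first prescriptions, but the gate refers to any U-200 patient. An HCP at a practice that only continues U-200 started elsewhere passes the gate and is then asked about something that does not happen there. Eligibility is broad enough for this to occur: Q5 admits HCPs who only provide education, Q6 admits registered nurses and other roles, and Q9 admits hospital staff. No HCP item asks whether the practice starts U-200.

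Such a respondent has no fitting answer. A No or I don't know then looks the same as a failure to counsel. The Protocol already accepts the principle, since it hides both items from HCPs with no U-200 patient, but the gate stops short of the endpoint's population.

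Q21 carries a further ambiguity. The letter travels in sample packs, and no HCP item asks whether the practice gives them out. HCPs who say at Q18 that they do not know of the letter skip to Q20 and still receive Q21.

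Q20 and Q21 are the only HCP items on discussion with patients, so the HCP side of the secondary objective rests on them.

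**Working it through.** **Inputs from the Protocol.** The target is 280 completed HCP surveys (section 5.7). Q11 caps completers with no U-200 patient at 140, a configurable number. At that cap, between 280 − 140 = 140 and 280 completers see Q20 and Q21.

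**Inputs not in the Protocol, so assumed.** These are the true rate π among HCPs to whom the item applies, the share s of those asked to whom it does not apply, and the share y of that group who still answer Yes.

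**The plan's own precision.** Equation 1 at n = 280 gives 1.96 × √(0.60 × 0.40 / 280) = 5.7 points at 60% and 1.96 × √(0.80 × 0.20 / 280) = 4.7 points at 80%. Both match Table 1. At n = 140 the same formula gives 8.1 and 6.6 points.

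**Effect of the mismatch.** With No and I don't know both kept in the denominator:

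observed = π × (1 − s) + y × s, so bias = s × (y − π).

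| True rate π | s | y = 0 | y = 0.5 | y = 1 |
|---|---|---|---|---|
| 60% | 10% | 54% | 59% | 64% |
| 60% | 20% | 48% | 58% | 68% |
| 80% | 10% | 72% | 77% | 82% |
| 80% | 20% | 64% | 74% | 84% |

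For example, π = 60%, s = 20% and y = 0 gives 0.60 × 0.80 = 48%.

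**Against sampling error.** With y = 0 and s = 20%, the loss is 12 points at π = 60% and 16 points at π = 80%. Both exceed the half-width even at n = 140. With s = 10%, the loss at 60% is 6 points, above the half-width at n = 280 (5.7) but below it at n = 140 (8.1). The loss at 80% is 8 points, above both 4.7 and 6.6.

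**Share needed to reach 50%, with y = 0.** s = 1 − 0.5/π, which is 16.7% at π = 60%, 37.5% at 80% and 44.4% at 90%.

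**Whether later analysis can repair it.** It cannot for Q20. The distinguishing fact is never collected, respondents cannot go back (section 5.6.1), and no queries are sent to them (section 5.8). For Q21, tabulating by Q18 and Q19 shows who knew of and read the letter, but not whether the practice starts U-200 or hands out samples.

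**The case against.** A reader might infer that the behaviour rates are biased downward, and that a real majority of counselling practices will be reported as a minority. The Protocol does not support either statement.

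- **Direction.** The bias is downward only if y is below π. Some HCPs to whom the items do not apply may still answer Yes, and section 5.11 acknowledges self-report bias. If all of them say Yes, a true 80% with s = 20% reads 84%.
- **Size.** Both items credit counselling by a colleague, so Q20 is inapplicable only where nobody at the practice starts U-200. That is a narrower group than HCPs who merely manage patients. The sampling list is the one used for the DHPC, which includes endocrinologists and primary care prescribers of mealtime insulin. Nothing in the Protocol shows that s is 10–20%.
- **Threshold.** The majority criterion in section 5.3 is worded for awareness of the messages, no hypothesis is tested, and higher true rates need a large s to fall to 50%.
- **Scoring.** Section 5.9 counts I don't know as incorrect for key-message questions. It does not say so for Q20 and Q21, which are also absent from the HCP answer key.

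A reader might also infer that practices without sample packs should be removed from Q21. The text points the other way. Section 3.1 describes giving out samples as routine, and section 5.11 treats reported non-receipt as the programme failing to disseminate its material. Removing these practices would flatter the measure. The argument has no bearing on Q20, which does not depend on the letter.

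These points defeat a claim of known direction or size. They leave the mismatch itself, because the gate still admits HCPs outside the endpoint's population and the survey has no way to identify them.

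**Conclusion.** The point holds as a denominator and interpretation problem. A No or I don't know on Q20 or Q21 cannot be split into failure to counsel and absence of first prescriptions, and the reported rates can be understated by an unknown amount. The 54–48% reading of a true 60%, and the 72–64% reading of a true 80%, assume s of 10–20% and y = 0. They illustrate what is possible and are not estimates. Only the secondary objective is affected, on the HCP side. For Q21, lack of sample packs is a genuine failure of the measure to reach patients and should be counted as such. It needs a label of its own because it calls for different action from an HCP who had the letter and did not discuss it. The change is worth making because it is cheap and the missing information cannot be recovered afterwards.

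**What to change.** Before the survey is programmed:

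1. Add to Q20 and Q21 the option *Not applicable: no patient has received an initial U-200 prescription at my practice*.
2. Base each behaviour rate on the HCPs to whom the item applies. Alongside it, report the not-applicable count and the rate over all who saw the item.
3. For Q21, record *my practice does not give out U-200 sample packs* as a separate reason. Keep these HCPs in the main Q21 denominator and show them as a distribution (reach) failure, apart from HCPs who had the letter and did not discuss it.

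The cost is one added option on each item, one added reason on Q21 and a denominator statement. The sample size does not change, although a rate among applicable HCPs rests on fewer respondents and has a wider interval. Some HCPs may choose not applicable to avoid saying No. The rate over all who saw the item bounds that effect.

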APPENDIX I.3 PATIENT SURVEY

SURVEY LEGEND

- **[PROGRAMMER]** is used to indicate directions to the programmer and is set in bold, red, uppercase letters between square brackets.
- **(INTERVIEWER)** is used to indicate directions to the telephone interviewer and is set in bold, blue, text between parentheses. This text appears when content is to be administered by telephone only (for example, spontaneous safety event reporting).
- **[ONLINE]** indicates a question/section is worded specifically for administering the survey online.
- **[TELEPHONE]** indicates a question/section is worded specifically for administering the survey over the telephone.
- **[BEGIN <Section>]** and **[END <Section>]** are used to indicate to the programmer the beginning and end of the survey or sections of text within the survey, for example, **[BEGIN PHONE PREAMBLE 1]** and **[END PHONE PREAMBLE 1]**.
- **[TERMINATE]** is displayed next to responses that should cause the survey to end. The following termination language will be programmed into the survey or read by the interviewer.

Thank you very much for your time today. Based on your answer, you are not eligible to take this survey. We appreciate your interest in the survey.
- **[RANDOMIZE LIST]** is inserted before questions to indicate to the programmer that the responses should be randomized. Responses such as “I don’t know,” “Prefer not to answer” or “None of the above” will always appear at the end of the randomized responses.
- **[GO TO Qx]** (skip logic) is inserted after a response to indicate to the programmer that the survey should skip to the indicated question (for example, **[GO TO Q17]** skips to question 17). If no skip logic is indicated the survey continues to the next question in the sequence.
- **[MULTILINE INPUT]** indicates to the programmer that multiple lines should be provided for data entry (for example, two address lines).
- **[FREE TEXT]** indicates to the programmer that one line should be provided for data entry.

SURVEY LEGEND

- **[DROP-DOWN LIST INPUT WITH STATES TABLE]** indicates to the programmer that the response should be a drop-down list containing the states in the table below.

Alabama	Georgia	Massachusetts	New York	Tennessee
Alaska	Hawaii	Michigan	North Carolina	Texas
Arizona	Idaho	Minnesota	North Dakota	Utah
Arkansas	Illinois	Mississippi	Ohio	Vermont
California	Indiana	Missouri	Oklahoma	Virginia
Colorado	Iowa	Montana	Oregon	Washington
Connecticut	Kansas	Nebraska	Pennsylvania	West Virginia
Delaware	Kentucky	Nevada	Rhode Island	Wisconsin
District of Columbia	Louisiana	New Hampshire	South Carolina	Wyoming
Florida	Maine	New Jersey	South Dakota	
	Maryland	New Mexico		

- The following is used to categorize survey populations into standard geographic regions but it is not displayed in the survey.

Geographic Distribution (based on address)¹: Northeast, Midwest, South, and West regions

Northeast Region

- New England Division - ME, NH, VT, MA, RI, CT
- Middle Atlantic Division - NY, NJ, PA

Midwest Region

- East North Central Division - OH, IN, IL, MI, WI
- West North Central Division - MN, IA, MO, ND, SD, NE, KS

South Region

- South Atlantic Division - DE, MD, DC, VA, WV, NC, SC, GA, FL
- East South Central Division - KY, TN, AL, MS
- West South Central Division - AR, LA, OK, TX

West Region

- Mountain Division - MT, ID, WY, CO, NM, AZ, UT, NV
- Pacific Division - WA, OR, CA, AK, HI

¹ U.S. Census Bureau, last revised Friday, 27-Jul-2001 12:59:43 EDT.

[BEGIN WELCOME PAGE]

This survey should take approximately 15 minutes to complete. If you cannot complete the survey at this time, please return when you can. Once you begin the survey you will need to answer all questions; you will not be able to access the survey again if you exit. Consider the following important information before you start the survey: the application will time out after 30 minutes of inactivity. If your session times out, you will not be able to log back into the survey to complete it and your participation in the survey will end.

If you are ready to begin the survey at this time, please click Continue. If not, click Return Later and return to this site when it is convenient for you.

Please note: Do not use the browser's back button during this survey.

[END WELCOME PAGE]

[BEGIN SCREENING QUESTIONS]

Please provide a response to all questions and statements.

1. Do you agree to take part in this survey about Humalog® KwikPen®, 200 units/mL (Humalog® U-200 KwikPen®)?
 - Yes
 - No **[TERMINATE]**

[Q2 - FOR WAVE 2 ONLY]

2. Have you ever participated in this survey for Humalog® U-200 KwikPen® before?
- Yes **[TERMINATE]**
 - No
 - I don't know **[TERMINATE]**
3. Have you been diagnosed with diabetes?
- Yes
 - No **[GO TO Q10, TERMINATE AFTER Q14]**
 - I don't know **[GO TO Q10, TERMINATE AFTER Q14]**
4. How long have you had diabetes?
- Less than 1 year
 - 1 – 5 years
 - 6 – 10 years
 - 11 – 15 years
 - More than 15 years
 - I don't know

5. Do you use injectable insulin to treat your diabetes?
- Yes
 - No **[GO TO Q10, TERMINATE AFTER Q14]**
 - I don't know **[GO TO Q10, TERMINATE AFTER Q14]**
 - I don't have diabetes **[GO TO Q10, TERMINATE AFTER Q14]**
6. For how long have you been using injectable insulin to manage your diabetes?
- Less than 1 year
 - 1 – 5 years
 - 6 – 10 years
 - 11 – 15 years
 - More than 15 years
 - I don't know **[GO TO Q10, TERMINATE AFTER Q14]**
7. Have you been prescribed Humalog® U-200 KwikPen® at least once?
- Yes
 - No **[GO TO Q10, TERMINATE AFTER Q14]**
 - I don't know **[GO TO Q10, TERMINATE AFTER Q14]**
 - I don't have diabetes/I don't use insulin **[GO TO Q10, TERMINATE AFTER Q14]**

8. For how long have you been using Humalog® U-200 KwikPen®?
- I have not used the Humalog® U-200 KwikPen® yet
 - Less than 3 months
 - 3 – 6 months
 - 7 – 12 months
 - More than 1 year
 - I don't know
 - I don't have diabetes/I don't use Humalog® U-200 KwikPen® **[GO TO Q10, TERMINATE AFTER Q14]**
9. What type of mealtime insulin did you use prior to using Humalog® U-200 KwikPen®?
- Humalog® U-100 KwikPen®
 - Other 100 Units/mL insulin
 - I don't know
 - I don't have diabetes/I don't use Humalog® U-200 KwikPen® **[TERMINATE AFTER Q14]**
10. What is your gender?
- Male
 - Female

11. What is the highest level of education you have completed?

- Less than high school
- Some high school
- High school graduate/GED (General Education Diploma)
- Some college/Associate's degree
- Bachelor's degree
- Master's degree
- Professional or Doctoral degree
- Prefer not to answer

12. In what state do you live?

[DROP-DOWN LIST INPUT WITH STATES TABLE, EXCLUDE PREFER NOT TO ANSWER]

13. Which of the following groups best describes your age?

- Under 18 **[TERMINATE AFTER Q14]**
- 18 – 29
- 30 – 39
- 40 – 49
- 50 – 59
- 60 – 69
- 70 or older
- Prefer not to answer **[TERMINATE AFTER Q14]**

14. Have you or any of your immediate family members ever worked for Eli Lilly and Company (Lilly), United BioSource Corporation (UBC), or the Food and Drug Administration (FDA)?
- Yes **[TERMINATE]**
 - No
 - I don't know **[TERMINATE]**

[END SCREENING QUESTIONS]

[BEGIN SURVEY CONTENT]

[BEGIN PREAMBLE 2 – DISPLAY ON SAME PAGE AS NEXT QUESTION]

The following questions are about Humalog® U-200 KwikPen®.

[END PREAMBLE 2]

15. Please answer True, False, or I don't know for each of the following statements about Humalog® U-200 KwikPen®.

	[RANDOMIZE LIST]	True	False	I don't know
A	Humalog® U-200 KwikPen® should only be injected using the prefilled KwikPen device in which it is supplied.			
B	Your dose of insulin does not need to be converted when changing from one strength of Humalog to the other (for example, changing from Humalog U-100 KwikPen to Humalog® U-200 KwikPen®).			

16. Please answer Yes, No, or I don't know for each of the following statements about the Patient Information Letter/*IMPORTANT SAFETY INFORMATION FOR* Humalog® KwikPen®, 200 units/mL, U-200 *insulin lispro* injection.

[RANDOMIZE LIST]		Yes	No	I don't know
A	The first time I was prescribed Humalog® U-200 KwikPen®, my doctor or nurse provided me with a paper copy of the Patient Information Letter/ IMPORTANT SAFETY INFORMATION . (This letter was included with the patient sample pen pack.)			
B	My doctor or nurse offered to explain information about the safe use of Humalog® U-200 KwikPen® the first time I was prescribed this product.			
C	I think about the important safety information for Humalog® U-200 KwikPen® to remind myself of the risks when injecting my insulin.			
D	I should always have a backup pen with me.			
E	It is ok to transfer insulin from the pen using a syringe.			

17. Other than the information you have received from your doctor or nurse, from what sources have you received and/or accessed information on the safe use and understanding of the Humalog® U-200 KwikPen®. (Please select all that apply.)

[RANDOMIZE LIST – KEEP OTHER AT THE BOTTOM]

- Pharmacist
- Other Healthcare Professional
- Diabetes Support Group
- Internet
- Product Warning Label
- Other

[TELEPHONE: BEGIN SAFETY EVENT/PRODUCT COMPLAINT – KEEP ON ONE PAGE]

(INTERVIEWER: Please record if respondent spontaneously reported a safety event or product complaint during the course of this interview.)

- Yes
- No **[GO TO CLOSING 1]**

Enter Safety Event or Product Complaint Verbatim

[MULTILINE INPUT]

(INTERVIEWER: Indicate to the respondent that someone may call back to ask more questions about the adverse event or product complaint that was reported.)

[END SAFETY EVENT/PRODUCT COMPLAINT]

[BEGIN CLOSING 1]

We would like to send you \$20.00 as compensation for your time and effort as well as a copy of the Patient Communication for Humalog® U-200 KwikPen®, and the correct answers to key safety message questions , but we need your name and address to do so. Do you agree to provide your contact information for this purpose?

- Yes
- No **[GO TO CLOSING 2]**

[END CLOSING 1]

[BEGIN CONTACT INFORMATION]

FIRST NAME: **[FREE TEXT]**

LAST NAME: **[FREE TEXT]**

MIDDLE INITIAL: **[OPTIONAL; MUST BE 1- ALPHA CHARACTER]**

ADDRESS: **[MULTILINE INPUT]**

CITY: **[FREE TEXT]**

STATE: **[DROP-DOWN LIST INPUT WITH STATES TABLE]**

ZIP CODE: **[MUST BE 5-DIGIT NUMERIC-ONLY]**

[END CONTACT INFORMATION]

[BEGIN CLOSING 2]

This completes the survey. Thank you again for your participation.

[END CLOSING 2]

[END SURVEY CONTENT]

[UBC LETTERHEAD]

[CURR_DATE]

[PAT_FIRST_NAME] [PAT_LAST_NAME]

[PAT_STREET_ADDR]

[PAT_CITY], [PAT_STATE] [PAT_ZIP]

Dear [PATIENT FULL NAME]:

On behalf of Eli Lilly and Company, the maker of Humalog® KwikPen®, 200 units/mL (Humalog® U-200 KwikPen®), we thank you for taking the time to complete the Humalog® U-200 KwikPen® Survey. To express our appreciation for your valuable time, enclosed is your \$20 gift card for your time and effort.

Additionally, for your information and to reinforce the key safety messages about Humalog® U-200 KwikPen® we have also enclosed two documents:

1. A copy of the Patient Information Letter/IMPORTANT SAFETY INFORMATION. Humalog® KwikPen®, 200 units/mL, U-200 insulin lispro injection
2. The correct answers to the key safety messages for Humalog® U-200 KwikPen®.

Lastly, please read the enclosed Terms and Conditions document before using your gift card as well as the privacy policy that can be found at: http://www.ctpayer.com/downloads/privacy_policy.pdf

Sincerely,

The Humalog® U-200 KwikPen® Survey Team

[name]

www.humalogsurveyus.com

Enclosed:

Gift Card, Terms and Conditions document and Frequently Asked Questions

Patient Information Letter/IMPORTANT SAFETY INFORMATION. Humalog® KwikPen®, 200 units/mL, U-200 insulin lispro injection

Correct Answers to Key Safety Messages

PATIENT CORRECT ANSWER DOCUMENT

Correct Responses to Select PATIENT Survey Questions about Key Safety Messages for Humalog® U-200 KwikPen®

Q: Please answer True, False, or I don't know for each of the following statements about Humalog® U-200 KwikPen®.

STATEMENT	Correct Response
Humalog® U-200 KwikPen® should only be injected using the prefilled KwikPen device in which it is supplied.	TRUE
Your dose of insulin does not need to be converted when changing from one strength of Humalog to the other (for example, changing from Humalog U-100 KwikPen to Humalog® U-200 KwikPen®).	TRUE

Q: Please answer Yes, No, or I don't know for each of the following statements about the Patient Information Letter/IMPORTANT SAFETY INFORMATION FOR Humalog® KwikPen®, 200 units/mL, U-200 insulin lispro injection.

STATEMENT	Correct Response
The first time I was prescribed Humalog® U-200 KwikPen®, my doctor or nurse provided me with a paper copy of the Patient Information Letter/IMPORTANT SAFETY INFORMATION. This letter was included with the patient sample pen pack.	Yes
My doctor or nurse offered to explain information about the safe use of Humalog® U-200 KwikPen® the first time I was prescribed this product.	Yes
I think about the important safety information for Humalog® U-200 KwikPen® to remind myself of the risks when injecting my insulin.	Yes
I should always have a backup pen with me	Yes
It is ok to transfer insulin from the pen using a syringe.	No

If you have questions or are unclear about any of these responses, please refer to the Patient Communication on Important Safety Information for Humalog® U-200 KwikPen®.

**APPENDIX I.5 DIRECT HEALTHCARE PROFESSIONAL COMMUNICATION ON
THE CORRECT USE OF Humalog® KwikPen®, 200 units/mL**

**APPENDIX I.6 PATIENT COMMUNICATION: IMPORTANT SAFETY
INFORMATION FOR HUMALOG® 200 UNITS/ML KWIKPEN®
(INSULIN LISPRO)**
